6.4.7 Treatment Allocation and Randomisation

All patients that accepted to take part in the study and freely signed the informed consent received an individual progressive screening number. Following the verification of all inclusion and exclusion criteria, a progressive randomisation number will be assigned to patients, which identified the patient for the entire study duration.

The randomization list will be in balanced-block design and will be prepared using a validated system that automates the random assignment of treatment groups to randomization numbers. Randomisation will be performed as a function of lists produced for the study, which provided the correct sequence

for the assignment of patients to the study groups and for the dispensation to patients of the treatment scheduled for the assigned group and as a function of the phase of the study.

In case of screening failure or study discontinuation, the screening and randomisation number could not be re-assigned to another patient and the patient will be not allowed to re-enter the study. Similarly, in case that a patient interrupted the participation in the study after the randomisation but before the start of use of the kit of the investigational product, this kit could not be assigned to another patient.

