3 INVESTIGATORS AND STUDY ADMINISTRATIVE STRUCTURE

The investigation will be conducted in 2 investigational sites in Italy. One more site in Italy will be opened, but no patients will be enrolled in this site.

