6.4.8 Blinding and Labelling

Not applicable, as this will be an open-label investigation.

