- Patient's anamnesis, with brief details of medical history and particular attention to medical history of upper symptoms (i.e. date of onset, symptoms' description, frequency and intensity of symptoms);
- Anamnesis of concomitant therapies, treatments taken in the last 4 weeks and ongoing treatments, with particular attention to remote and recent therapies, intake of PPIs and/or medical devices and/or similar products (e.g. alginates, antacids, etc..), chronic use of drugs that interfere with the salivary secretion (e.g. anti-histamines or inhaled steroids) and thus represented an exclusion criterion and other non-permitted therapies;
- Objective examination and concomitant diseases;
- Haematology and blood chemistry: haemochrome, erythrosedimentation rate (ESR), C-reactive
 protein (CRP), aspartate aminotransferase (AST), alanine aminotransferase (ALT), alkaline
 phosphatase, gamma-glutamyl transpeptidase (gamma-GT), total and direct bilirubin, glycaemia,
 creatininemia, blood urea nitrogen (BUN) (tests performed in the last 3 months will be kept as
 valid);

- The evaluation of beta-human chorionic gonadotropin (beta-hCG) levels will be performed only in women of childbearing potential;
- RSI questionnaire, completed by patients following the Investigator's explanation;
- Likert scale, completed by patients following the Investigator's explanation.

Furthermore, the Investigator:

- Explained to patients which other products could or not could be taken for the entire study duration;
- Dispensed a diary to patients, to be completed daily, explaining to patients the procedures for completion and the importance of a correct filling, recommending them to daily report the presence and intensity of upper symptoms, the amount of taken investigational product, the possible use of other products taken on-demand for the treatment of GERD and of all other products, the possible changes of dose of taken treatments and all possible adverse events or incidents occurred during the study.

Patients satisfying inclusion/exclusion criteria and that, by signing the informed consent provided at the beginning of the study, accepted to adhere to the study procedures and to complete the daily diary, will be included in the study and will be randomly allocated to the investigational product to be taken for the following 6 weeks of treatment. Thus the Investigator proceeded to:

- Patient's randomisation and assignment of a randomisation number;

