- Assessment of patients responder/non-responder to investigational products;
- End of study assessments.

Furthermore, the Investigator:

- Selected responder patients in Group 1 and treated with Gerdoff®+PPI;
- In case the patient will be willing to continue in the study, dispensed a new diary to the patient, to be completed daily for the 12-week follow-up period, further explaining the procedures of completion and the importance of a correct completion to patient, and recommending him/her to report daily the presence and intensity of upper symptoms, the amount of administered investigational product, the possible use of other products taken on-demand for the treatment of GERD, and all the other products taken, and all the possible adverse events or incidents occurred during the study.

Responder patients Group 1 (Gerdoff®+PPI) that, by signing the informed consent at the beginning of the study, accepted to attain the procedures scheduled for the follow-up period and to continue to complete the daily diary will be then included in the follow-up period (starting from visit V4) and will be randomly assigned to dispensing of product adequate for the next 12 weeks or to control group (i.e. no treatment). All patients included in the follow-up period received a dispensing of omeprazole adequate for the next 12 weeks, to be taken as rescue medication only if necessary and according to the Investigator's indications. The investigator explained to patients when and why omeprazole could be taken and that the intake and the reason will be to be reported in the daily diary. Then the investigator proceeded to:

- Patient's randomisation to Gerdoff® group or control group;
- Dispensing of the kit of Gerdoff® for the following 12 weeks of treatment to patients randomised in this group;
- Dispensing of the kit of omeprazole for the following 12 weeks of treatment to patients that continued in the follow-up period;
- Registration in the source document and in the eCRF of the number of product kit dispensed to responder patients in Group 1 that continued in the follow-up period;
- Registration in the source document and in the eCRF of the number of kit of omeprazole as rescue medication dispensed to all patients that continued in the follow-up period;
- Recommendation to take the first dose of investigational products in the morning of the day following Visit V4;

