8.1 Sample Size Justification

Although a search in literature has not identified any published article for trials that used the same investigation design as that used in the present study, some recently published articles (9, 13-15) allowed to formulate a sample size calculation for the present investigation.

The calculation of the sample size will be based on the primary objective of the investigation, i.e. to assess the change of RSI questionnaire from baseline to 6 weeks of treatment in the two treatment arms, Gerdoff®- PPI and PPI alone, based on an hypothesis that the addition of Gerdoff® to PPI could improve the effect of disappearance and of rapidity of control of upper symptoms of GERD. Such effect will be evaluated as the mean change in RSI compared to baseline, taking into consideration the variable age, standard deviation (SD) and expected value after treatment with omeprazole.

The following assumptions will be made for the sample size calculation:

Difference between the two arms (delta): 3.6; SD of the difference: 5.

Based on these assumptions, for a comparison based on unpaired Student t test, at a power of 80% and a level of probability of 5% for a two-tailed test, 62 patients (31 in each treatment arm) will be to be included in the study. Estimating a drop-out rate of 20%, 78 patients (39 in each treatment arm) will be to be included in the study.

The software PS Power and Sample Size Calculations Version 3.0, January 2009, will be used for the sample size calculation.

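### No step conceals the next assignment: the recruiting investigator randomises open-label from balanced-block lists, so foreknowledge or prediction of the V1 allocation cannot be excluded

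*Combined protocol and SAP*

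**What the plan says.** Section 6.4.7: "The randomization list will be in balanced-block design and will be prepared using a validated system". It adds: "Randomisation will be performed as a function of lists produced for the study, which provided the correct sequence". A progressive number is given once the entry criteria have been checked. The validated system is described only as producing the list, not as releasing assignments.

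Section 6.5.2, Visit 1: the gastroenterologist investigator verifies the criteria, explains the RSI to the patient, and then carries out the patient's "randomisation and assignment of a randomisation number". Section 6.5.2, Visit 4: the investigator assesses response, selects Group 1 responders who are willing to continue, and performs the "randomisation to Gerdoff® group or control group".

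Section 6.4.8 on blinding: "Not applicable, as this will be an open-label investigation". Section 3: "The investigation will be conducted in 2 investigational sites in Italy".

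No section says who holds the lists, how or when an assignment is revealed, how large the blocks are, whether their size varies, or whether there is a list per site.

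**The concern.** Blinding and allocation concealment are separate safeguards. An open-label trial gives up the first but can keep the second. Here the person who decides whether a patient enters also draws the next place on the list and knows every earlier allocation at the site. Balanced blocks make the sequence partly predictable from its past, and a list held on site could simply be read.

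Entry leaves some room for judgement. Section 6.3.2 has an exclusion based on the investigator's opinion, and section 6.3.1 asks for cooperative patients. The RSI threshold of 20 is scored at the same visit as randomisation, and that score is also the baseline of the primary endpoint.

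If the kind of patient admitted differs with the expected arm, the arms differ in prognosis before treatment starts. The primary analysis in 8.3.1 is a t-test on RSI change with no term for baseline or site, so such a difference passes into the estimated effect.

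**Working it through.** **Inputs from the plan.** 1:1 open-label allocation (6.1); two enrolling sites (3); 78 patients, 39 per arm (8.1); "Difference between the two arms (delta): 3.6; SD of the difference: 5"; "at a power of 80% and a level of probability of 5% for a two-tailed test".

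**The plan's own figure.** Taking 5 as the SD of RSI change within an arm, n per arm = 2(1.960 + 0.842)² × 5² / 3.6² = 2 × 7.85 × 25 / 12.96 = 30.3, rounded up to 31, so 62 in all. For dropout, 62 / (1 − 0.20) = 77.5, rounded up to 78. Both figures reproduce, and this point does not change them.

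**Assumptions, since the plan is silent.** Block size 2, 4 or 6; either one list per site or one list shared by two sites of equal recruitment; steering of h = 1 or 2 RSI points in expected change, in the direction of the guess, for every patient where one arm looks more likely.

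**Predictability with a list per site and a known block size.** Worked for a block of 4:

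- Certain assignments: of the six possible orders, two (AABB, BBAA) make the last two places certain and four make only the last certain. That is (2×2 + 4×1) / (6×4) = 8/24 = 33%.
- Best guess: place 1 is right with probability 1/2; place 2, 2/3; place 3, 1/3 × 1 + 2/3 × 1/2 = 2/3; place 4, 1. The mean is 2.833/4 = 71%.

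The same enumeration gives 50% certain and 75% correct for blocks of 2, and 25% and 68% for blocks of 6.

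**Bias.** Let a be guess accuracy, counting ties as one half. The net pull toward the true arm is 2a − 1. The mean shift is +h(2a − 1) in one arm and −h(2a − 1) in the other, so the bias is 2h(2a − 1). For a block of 4 and h = 1: 2 × (2 × 0.7083 − 1) = 0.83 points.

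**Type I error.** Simulated null trials (78 patients, SD 5, two-sided t-test at 5%, 4,000 replicates). In the rows with block size unknown, and in the shared-list row, the guess is whichever arm is behind among the site's own patients.

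| List | Block | Accuracy | Bias, h=1 | Type I, h=1 | Bias, h=2 | Type I, h=2 |
|---|---|---|---|---|---|---|
| By site, size known | 2 | 75% | 1.0 | 14% | 2.0 | 39% |
| | 4 | 71% | 0.8 | 11% | 1.7 | 26% |
| | 6 | 68% | 0.7 | 9% | 1.5 | 24% |
| By site, size unknown | 2 | 74% | 0.9 | 12% | 1.9 | 38% |
| | 4 | 70% | 0.8 | 11% | 1.6 | 26% |
| | 6 | 68% | 0.7 | 9% | 1.4 | 22% |
| By site, size unknown | 4 and 6 mixed | 69% | 0.7 | 10% | 1.5 | 24% |
| Shared, own patients only | 2 to 6 | 54% | 0.1–0.2 | 5% | 0.3 | 6–7% |

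The biases with size known come from the formula. The table analyses all 78. Simulation error and a smaller analysed number (nearer 62) lower the bottom of the site-list range a little, so I quote it as about 8–14% for h = 1 and 19–39% for h = 2.

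**Reading.** Mixing block sizes within site-specific lists hardly helps (69%). What brings guessing close to chance is that neither site sees the whole sequence.

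**The case against.** A reader might infer that upcoming allocations can be deduced. The documents do not support that. Certainty is limited to 50%, 33% or 25% of assignments, and only if lists are by site and the fixed block size (2, 4 or 6) is known. None of this is stated. Nor does the plan say that lists are unstratified by site; it is silent. If they are unstratified, the mild shared-list row applies, so the large rejection rates cannot be combined with that reading. This objection stands, and it is why the claim is that prediction cannot be excluded.

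The size of steering is also assumed. If only a quarter of guesses were acted on by 1 point, the bias for blocks of 4 would be 0.83 / 4 = 0.2 points, with rejection close to nominal. The RSI is completed by the patient, so explaining it does not amount to controlling the score. Adjustment for baseline could remove the part of any imbalance carried by measured factors, though 8.3.1 plans none and unmeasured factors would remain.

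A reader might also give V4 equal weight. Response there is a numeric rule (RSI fall of at least 50% and a score below 13), and 8.3.2 makes follow-up efficacy descriptive only. Selection through willingness to continue could distort the described groups, but it affects no planned test.

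None of this supplies the missing step. The favourable shared-list case is not documented either.

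**Conclusion.** The gap is real and bears on the primary comparison. Followed as written, the plan has the recruiting investigator verify eligibility and then randomise open-label from balanced-block lists, with nothing to hide the next assignment. Whether that allows real prediction depends on facts the plan omits. Under the stated assumptions the consequence runs from slight (shared list) to a bias of more than half the planned 3.6 points (site lists, blocks of 2, 2-point steering: 2.0 / 3.6 = 56%).

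The prediction figures do not cover a list that the investigator can read directly, which would be worse. The shared-list figures assume two sites of similar recruitment; if one site enrols nearly everyone, it sees nearly the whole sequence. This is not evidence that steering would happen. It is a weakness that costs little to close beforehand and is hard to repair afterwards.

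**What to change.** In 6.4.7, for both randomisations:

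1. State that sites hold no list.
2. State that the eCRF (already validated under 7.4) or another central system releases the V1 allocation only after eligibility and the V1 RSI are entered and locked. At V4, release it only after responder status and agreement to continue are locked.
3. Use one central list across both sites, with varying block sizes withheld from the sites. Do not use site-stratified blocks: locking prevents reading ahead but not guessing from past open allocations, and mixed blocks of 4 and 6 by site remain about 69% guessable.
4. In 8.3.1, include site as a factor in the primary comparison.

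The cost is eCRF configuration and a new list before first enrolment, eCRF access at the visit before dispensing, possibly a slight imbalance of arms within a site, and one degree of freedom. The sample size stays at 78.

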6.4.8 Blinding and Labelling

Not applicable, as this will be an open-label investigation.

6.5 Study Procedures and Study Schedule

6.5.1 Overview of Data Collection

The study plan and scheduled examination and procedures are summarised in the following flow-chart (Figure 2).

Figure 2. Flow-chart of the study

Visit	V1 Baseline	V2 (intermediate visit)	V3 (intermediate visit)	V4 ^(a) End of study/ Early interruption ^(c)	V5 ^(b) Follow-up (control visit) ^(d)	interruption ^(c)
Period	Т0	T 1 1 week ± 1 day	T 3 3 weeks ± 2 days	T6 6 weeks ± 2 days	T12 12 weeks ± 3 days	T18 18 weeks ± 3 days
Informed consent	X		•	-	Ĭ	•
Inclusion/exclusion criteria	X					
Demographic data	X					
Vital signs	X			X		X
First GERD diagnosis or diagnosis confirmation	X					
Anamnesis	X					
Reference. ENT specialist	X					
Objective examination and concomitant diseases	X			X		X
Assessment of symptoms	X	X	X	X	X	X
Haematology and blood chemistry	X			X		X
Beta-hCG (1)	X			X		X
Treatment dispensing Gerdoff® + PPI or PPI	X					
Treatment dispensing Gerdoff®/no treatment and rescue (2)				X		
Concomitant therapies	X	X	X	X	X	X
Likert scale	X	X	X	X	X	X
RSI questionnaire	X	X	X	X	X	X
Diary dispensing/returning	X	X	X	X	X	X
Questionnaire of treatment likelihood		X	X	X		
Assessment of responder/ non-responder patients				X		
Assessment of maintenance of the effect						X
Incidents/adverse events		X	X	X	X	X

Visit	V1 Baseline	V2 (intermediate visit)	V3 (intermediate visit)	V4 ^(a) End of study/ Early interruption ^(c)	V5 ^(b) Follow-up (control visit) ^(d)	V6 ^(b) End of follow- up/Early interruption ^(c)
Period	Т0	T 1 1 week ± 1 day	T 3 3 weeks ± 2 days	T6 6 weeks ± 2 days	T12 12 weeks ± 3 days	T18 18 weeks ± 3 days
Assessment of compliance to Gerdoff® and PPI, and product accountability				X		
Assessment of compliance to Gerdoff® and product accountability						X
Use of rescue medication (3)		X	X	X	X	X
End of study visit				X		
End of follow-up visit						X

- (a) End of study visit for all patients included in the study. Responder patients included in Group 1 (Gerdoff®+PPI) immediately continued the study with the follow-up phase.
- (b) Only responder patients included in Group 1 (Gerdoff®+PPI) will be included in the follow-up phase.
- (1) Only in childbearing potential women.
- ⁽²⁾ Only in responder patients in Group 1 that took part in the follow-up study.
- Ouring the first 6 weeks of treatment the use of any type of rescue medication will be not permitted in both treatment groups. The possible intake of rescue medication during the first 6 weeks of the study will be to be considered as a protocol violation. During the follow-up phase only the use of omeprazole as rescue will be permitted as rescue medication, at constant dose and only if necessary, in both the group of untreated patients (control group) and the group of treated patients, whereas the use of other products for the treatment of GERD will be not permitted. In case of intake patients will be to be considered as protocol violators and will be to be discontinued from the study. The possible rescue medications used during the overall study period will be to be recorded in the source documentation and in the eCRF.
- (c) In case of early study discontinuation the patient will be to be considered as a treatment failure and the investigator had to do all the possible to perform:
 - End of study assessments, scheduled at visit V4, in case the patient interrupted the study during the 6-week treatment period;
 - End of follow-up period assessments, scheduled at visit V6, in case the patient interrupted the study during the 12-week follow-up period.
- (d) Visit V5 could be also performed as phone visit, only if agreed with the patient at Visit V4, during which the Likert scale and the RSI questionnaire for the visit V5 and the daily diaries for the visits V5 and V6 will be to be handed to the patient. At visit V6, the patient had to return them to the Investigator.

Study periods

The study plan included two consecutive study periods:

Treatment period

From Visit V1 to Visit V4, in which randomised patients took Gerdoff® + PPI (omeprazole) or PPI (omeprazole) for a period of 6 weeks. During the treatment period patients attended 4 scheduled visits: Visit V1 will be the baseline visit for patients' inclusion in the study, Visits V2 and V3 will be intermediate visits for the evaluation of the effects of treatment, and Visit V4 will be the end of study visit in which patients will be classified as responders or non-responders.

• Follow-up period

From visit V4 to visit V6, in which patients classified as responders and belonging to Group 1 (Gerdoff® + PPI) will be randomised to treatment with Gerdoff® or to the control group (untreated group). All patients included in the follow-up period received a packaging of omeprazole as rescue medication, to be taken only if necessary at constant dose and according to the indications of the Investigator. The follow-up period lasted 12 weeks. During the follow-up period, patients performed, in addition to visit V4, other two scheduled visits. Visit V5 will be an intermediate visit for the evaluation of the effects of treatment (which could be performed by phone), and visit V6 will be the end of treatment visit, in which the effects of the maintenance of treatment will be evaluated.

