6.3.3 Removal of Patients from Therapy or Assessment

Patient withdrawal

Patients had the right to withdraw from the study at any time for any reason including personal reasons (consent withdrawal). The Investigator also had the right to withdraw any patient from the study if he/she deemed this appropriate and in the best interest of the patients.

The following necessitated the discontinuation of a patient from the study:

- Voluntary subject withdrawal for any reason, even if not motivated;
- Appearance of an adverse event that could put at risk the patient's health;
- Sponsor's decision (to be justified);
- Investigator's decision (to be justified), in the patient's best interest;
- Poor patient's compliance to scheduled study visits and/or study procedures,
- Worsening of clinical general conditions requiring the discontinuation of the study;

- Major protocol violations (e.g. intake of any other therapy for GERD, irrespective of dose and frequency of administration);
- Poor adherence to inclusion/exclusion criteria that emerged after the inclusion of a patient and that will not guarantee the patient's safety.

The reasons for the interruption or the exclusion of a patient from the study had to be reported in the eCRF section 'End of study form' or 'End of follow-up period form' and will be to be communicated to the study sponsor.

In the case of early study discontinuation, the patient will be to be considered as a treatment failure. However, the investigator had to make any effort to perform the end of study assessments, scheduled at visit V4, in case a patient interrupted the study during the 6-week treatment period, or scheduled at visit V6, in case a patient interrupted the study during the 12-week follow-up period.

In the discontinuation visit, the patient had to return the investigational product and the daily diary completed up to the time of discontinuation.

The investigator had to record the reasons for the patient's treatment discontinuation and the early study conclusion in the clinical record/worksheet and in the eCRF. The sponsor had to be timely informed.

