6.5.3 Study Endpoints

Primary performance variable

The primary performance variable of the study will be the change from baseline to visit V4 of the total score of RSI questionnaire, used to assess the effect of treatment on upper symptoms. The RSI questionnaire examines 9 items, to be scored from 0 to 5, with a higher score indication a higher severity of the symptom (range of total score: 0-45).

Secondary performance variables

The secondary performance variables of the study will be:

- Change of the total score of RSI questionnaire from baseline to the other time points;
- Change of the score of single items of the RSI questionnaire from baseline at any time point;
- Number and percentage of responder/non-responder patients at end of treatment (visit V4);
- Change from baseline to end of treatment (visit V4) and end of follow-up (visit V6) of upper symptoms, assessed using the Likert scale. The Likert scale scored symptoms from 0 to 4, with a higher score indication a higher frequency of the symptom;
- Presence of upper symptoms at baseline, end of treatment (visit V4) and end of follow-up (visit V6), assessed using the RSI questionnaire and the Likert scale:
- Use of rescue medication during the follow-up period: administered therapy, frequency of administration, timing of administration and administered dose;
- Patient's opinion of satisfaction with treatment, requested at intermediate Visits V2 and V3, and at the end of treatment visit V4, by means of a semiquantitative ordinal scale, where: 0 = low, 1 = discrete, 2 = good, 3 = excellent.

Safety variables

The safety variables of the study will be:

- Frequency of adverse events and incidents occurring at any time, during the study;
- Changes from baseline of haematology and blood chemistry parameters;
- Changes from baseline of vital signs (weight, BMI, blood pressure, heart rate and respiratory rate).

Incidents and adverse events

Incidents

According to MEDDEV 2.12.1, Rev. 8, a medical device incident is defined as 'any malfunction or deterioration in the characteristics and/or clinical performance of a device, as well as any inadequacy in the labelling or the instructions for use, which, directly or indirectly, might lead to or might have

led to the death of a patient, or a user or of other persons or to a serious deterioration in their state of health'.

A medical device incident that required reporting included:

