8.3.1 Primary Performance Analysis

In the analysis of primary performance variable, i.e. the mean difference from the baseline (delta) of the RSI score measured after 6 weeks of treatment, the two treatment groups will be compared using a Student's t-test for independent data.

The test results will be tabulated with the appropriate descriptive statistics and with the calculation of the 95% CI of the difference relative to the delta between the two study treatments.

The primary objective of the study will be achieved only if the statistically significant difference between the two study treatments with the current delta value will be coincident with that planned in the calculation of the numerosity, i.e. 3.6.

Sensitivity analyses will be conducted on the primary performance variable. The study of the temporal profile of the RSI questionnaire will be performed using the analysis of variance for repeated measures (ANOVA). In addition to the treatment effect, the time effect and the treatment by time interaction will be included in the model.

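### Patients who stop during the 6-week period are handled inconsistently: their RSI may stand as the V4 value, they may be excluded, or they are treatment failures with no analysis rule

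*Combined protocol and SAP*

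**What the plan says.** **Collection.** In the flow-chart (6.5.1, Figure 2), one column serves both the V4 end-of-study visit and early interruption. It is timed at 6 weeks ± 2 days and the RSI is marked in it. Note (c) asks the investigator to try to obtain, after an early stop, "End of study assessments, scheduled at visit V4, in case the patient interrupted the study during the 6-week treatment period". Section 6.3.3 makes the same request.

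**Status.** Section 6.3.3 says that on early discontinuation "the patient will be to be considered as a treatment failure", and note (c) repeats this.

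**Primary variable and test.** Section 6.5.3 defines it as "the change from baseline to visit V4 of the total score of RSI questionnaire", with no day window. Section 8.3.1 describes it as "the mean difference from the baseline (delta) of the RSI score measured after 6 weeks of treatment" and compares the arms with an independent-samples t-test.

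**Population.** Section 8.2 places all efficacy analyses, and again the primary one, on ITT: randomised patients with at least one dose. The same section then says that patients below 95% of the 6-week dosage are left out of the primary analysis and appear in a sensitivity analysis instead.

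**Responders.** Section 8.3.2 classifies by score alone: at least a 50% fall from baseline and a value below 13. Early discontinuation is not mentioned.

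**The concern.** Three statements point to three different treatments of the same patient: included with the exit RSI, excluded, or failed. The two descriptions of the primary variable, change to V4 and score after six weeks, mean the same thing for a completer. They diverge for someone who leaves in week 2 and completes the V4 assessments that day.

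The failure label is never turned into a value for a continuous RSI change. It is also not carried to the endpoint that it fits: a patient who leaves early with a low score is a failure under 6.3.3 and could be a responder under 8.3.2.

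The number of patients affected is not small, since 20% drop-out is planned. Allocation is open-label, and some of the listed reasons for discontinuation (clinical worsening, taking another GERD therapy) are related to outcome. Stopping could therefore differ by arm, and the choice among the three treatments could be made after the data are seen.

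**Working it through.** **1. The plan's own sample size.** Inputs from 8.1: "Difference between the two arms (delta): 3.6; SD of the difference: 5", "at a power of 80% and a level of probability of 5% for a two-tailed test".

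n per arm = 2 × (1.960 + 0.842)² × 5² / 3.6² = 30.3, so 31. This agrees with "62 patients (31 in each treatment arm) will be to be included in the study". Inflating, 62 / (1 − 0.20) = 77.5, so 78, which agrees with "Estimating a drop-out rate of 20%, 78 patients (39 in each treatment arm) will be to be included in the study". Exact noncentral-t power at 31 per arm is 79.6%. The sizing therefore treats drop-outs as contributing nothing, and the benchmark for power is the planned 80%.

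**2. Whom the 95% rule removes.** Full dosing is 42 days. Stopping after 39 days gives 39/42 = 92.9%; after 40 days, 40/42 = 95.2%. The V4 window opens at day 40 (42 − 2). A patient who stops treatment before then is below 95% and is excluded under that sentence of 8.2.

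**3. Early values analysed as V4: power.** Assume that 20% stop in each arm, all of them give an exit RSI, those values carry a fraction f of the 3.6-point difference, and the SD stays at 5. The analysed difference is 0.8 × 3.6 + 0.2 × f × 3.6.

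| f | Difference | Power, 39 per arm |
|---|---|---|
| 0 | 2.88 | 71% |
| 1/3 | 3.12 | 78% |
| 2/3 | 3.36 | 83% |

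Holding the SD at 5 is favourable, because mixing early and week-6 values adds spread. For example, let PPI completers improve by 8 points and combination completers by 11.6, with early values holding half of that. The variances become 25 + 0.16 × 5.8² = 30.4 and 25 + 0.16 × 4² = 27.6, a pooled SD of 5.38. The difference is 3.24, and power is 75% rather than the 81% obtained with SD 5.

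**4. Unequal stopping: bias.**
- *Early values used.* If they fall g points short of the same patients' week-6 improvement, each arm's mean is lowered by (proportion stopping) × g. With 15% versus 25% stopping and g = 5 to 10, the difference shifts by 0.10 × 5 = 0.5 to 0.10 × 10 = 1.0 points, or 14% to 28% of 3.6. More stopping on PPI alone inflates the difference; more stopping on the combination shrinks it.
- *Patients excluded.* If discontinuers would have improved by g points less than completers at week 6, dropping them raises each arm's mean by (proportion stopping) × g. The same split and gap give the same 0.5 to 1.0 points, in the opposite direction.

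**5. A wider split, early values used.** With 8 and 11.6 points as in step 3 and half retained, 10% stopping on combination versus 30% on PPI gives 11.6 × 0.95 − 8 × 0.85 = 4.22. The reverse gives 11.6 × 0.85 − 8 × 0.95 = 2.26. The true difference is 3.6 in both.

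The stopping splits, gaps, retained fractions and 8-point improvement are assumptions; the documents give none of them.

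**The case against.** A reader might infer that the plan puts the early RSI into the primary t-test. The documents do not say so. The flow-chart is a schedule of procedures, and the V4 assessments requested at an early stop also include vital signs, laboratory tests and product accountability. Section 8.3.1 speaks of six weeks of treatment, and the 95% sentence would keep nearly all these patients out. This objection stands: inclusion is what the ITT statement and the shared column permit, not a stated data rule.

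A reader might also infer that failure status and an exit RSI are mutually exclusive. They are not: one is a category and the other a measurement, and both can be recorded. What is missing is any analysis that uses the category.

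A third tempting reading sets 71% to 83% power against the 88% that 39 analysed patients per arm would give at 3.6 points. The trial was planned for 80% with 31 per arm, so the loss is modest and absent in the mildest case. The scenarios also suppose that every discontinuer supplies an exit RSI, whereas the plan promises only an effort.

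Finally, section 8 refers to a final SAP, version 1.1 (Annex 10), whose separate text was not available for this review. A window rule there cannot be ruled out.

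None of this resolves the inconsistency. The 95% exclusion contradicts the ITT statements in its own section and selects on a post-randomisation criterion. It also sends the same patients, still without a visit window, into the sensitivity analysis.

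**Conclusion.** The point holds as an inconsistency in the handling of early discontinuers, and the plan should be changed. Depending on which sentence is followed, they are analysed with a mistimed value or dropped for low intake after randomisation; their failure status is applied in neither 8.3.1 nor 8.3.2.

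Bias is the larger risk: 0.5 to 1.0 points on a planned 3.6, by either route, under an assumed 15% versus 25% split and a 5 to 10 point gap. It can go in either direction, and it is near zero if stopping and gaps are equal in both arms. Power is the smaller issue: about 71% to 83% against 80% if early values are used and carry none to two thirds of the effect at SD 5. Exclusion at the planned rate leaves it at the planned level.

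**What to change.** Amend 6.5.3, 8.2, 8.3.1 and 8.3.2 so that one rule applies:

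1. An RSI counts as the V4 value only if taken at 6 weeks ± 2 days.
2. All ITT patients stay in the primary analysis; the 95%-dosage restriction becomes a sensitivity analysis.
3. The week-6 difference is estimated from a mixed model over V2, V3 and V4, with treatment, visit, their interaction and baseline RSI as covariate. Section 8.3.1 already plans a repeated-measures analysis, and the RSI is collected at every visit.
4. An early-exit RSI is used at V2 or V3 only if it falls in that visit's window and the visit has no value; otherwise it enters a sensitivity analysis only. A patient leaving in week 5 will usually have a V3 value already, so the exit score should not be forced into that slot.
5. Early discontinuers count as non-responders at V4 in 8.3.2.
6. One sensitivity analysis sets their RSI change to 0 in both arms, which gives the failure status a defined meaning for the primary variable.

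The cost is wording, a visit-window derivation and modest programming, with no new data. The mixed model relies on data being missing at random; the sensitivity analysis in item 6 probes that assumption.
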